The gingivitis index is based on the Gingival Index system,² in this case, the global gingival index is GGI. The GGI was also significantly higher for the test group (Group X) at the initial visit; for the test group (Group X) = 2.03 (0.025) and GGI for the control group (Group A) = 1.91 (0.035), ($t = -2.89$, $df = 55$, $p = 0.006$). Figure 6 illustrates a potential interaction between treatment and time of observation that required statistical consideration and control. Again, GGI for visit 1 was used as a covariate so as not to over-estimate treatment effects on GGI represented in a time-by-treatment interaction. The ANCOVA upheld a statistically significant ($t = 2.12$, $df = 51$, $p = 0.039$) between treatments. Boxplots of the GGI across visits is shown in Figure 7. The test group (Group X) reduction in GGI was 27.3% versus the control group's (Group A) reduction of 20.4%, also statistically significant difference by repeated measures analysis of variance ($F = 8.141$, $df = 1$, $p = 0.0046$).

[figure not shown]

Figure 6. Interaction plot showing group assignment interacting with time on gingival index measures (GGI).

[figure not shown]

Figure 7. Boxplots of gingival index measures comparing treatment control group (Group A) and test group (Group X). Test group (Group X) started with higher gingival index levels. Gingival index decreased more and faster in test group (Group X) than in the control group (Group A), though both decreased significantly.

Differential Effects of Mouthwashes on Implants in Control Group (Group A) and Test Group (Group X)

Of particular interest was the specific effect that control mouthwash (rinse A) and test mouthwash (rinse X) might have on implant and non-implant sites across the three outcomes. Table 4 illustrates the overall study results of treatments and implants on the three outcomes. Probing depth was not different between treatments for implant and non-implant sites. Plaque and gingival indexes were improved significantly under test rinse Treatment (rinse X), with details described in Tables 5, 6, and 7 below. In addition, implant sites improved at a faster rate under test rinse Treatment (rinse X) conditions for both gingivitis and plaque.

Table 4. Omnibus test for main effects and interactions of control mouthwash (rinse A) and test mouthwash (rinse X) on implant and non-implant sites.

Sites of Implants responding differently to treatment					
All outcomes: measures in table					

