Transformed Variable: Average outcomes					
Source	Type III Sum of Squares	df	Mean Square	F	Sig.
Intercept	2790.339	1	2790.339	9371.807	0.000
Implant	2.916	1	2.916	9.793	0.002
Measure	13.625	1	13.625	45.761	0.000
Group	1.954	1	1.954	6.562	0.011
Implant * measure	7.58	1	7.58	25.459	0.000
Implant * group	0.018	1	0.018	0.061	0.805
Measure * group	8.331	1	8.331	27.981	0.000
Implant * measure * group	16.127	1	16.127	54.166	0.000
Error	60.738	204	0.298		

Implants and Probing depth

Probing depth scores (PDS) were only collected at initial and last observations visits 1 and 4. At intake, control group (Group A) patients had significantly higher levels of probing depth around implanted teeth (mean = 2.93, SEM = 0.094) than in non-implanted teeth (2.69, 0.063), with $t = 2.31$, $df = 53$, $p = 0.025$. In addition, control group (Group A) implant site probing depth was greater at intake than for test group (Group X) probing depth at implanted sites, 3.40 (0.109) versus 2.45 (0.080) respectively, with $t = 7.07$, $df = 52$, $p < 0.001$.

[figure not shown]
Table 5 represents the results in an overall test of significance with PDS as a dependent variable. There were two notable interactions. One was a time by group interaction, representing that probing depths changed significantly differently over time. Another was a three-way interaction time-by-implant-by-group assignment. The time-by-group interaction was seen before in the PDS score and while significant, the actual difference was less than 1%. The three-way interaction is a false signal in that implant scores probe scores increased slightly in the test group (Group X) and decreased slightly in the control group (Group A) – and neither change was significant.

Probing depth scores for implant and non-implant sites did not change significantly in both groups did not change significantly in both implant and non-implant sites as observed over time for both groups. Figure 8 illustrates the lack of change in implant and non-implant depth scores in either group.

Table 5. Summary results of general linear model of probing depth measures for implant sites over time.

Tests of Within-Subjects Contrasts					
Measure: GGI					
Source	Type III Sum of Squares	df	Mean Square	F	Sig.
Time	15.113	1	15.113	563.159	0.000
Time * implant	1.507	1	1.507	56.172	0.000
Time * group	0.941	1	0.941	35.047	0.000
Time * implant * group	0.001	1	0.001	0.041	0.840
Error(Time)	2.737	102	0.027		

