Figure 8. No differential effects of mouthwashes on probing depth between implant and non-implant sites. Both groups showed only slight decreases in probing depth. Note that in control condition (rinse A), probing depth was higher for the implant group at baseline.

Implants and Gingival Index

Implant versus normal oral sites also showed a significant main effect ($F = 79.0$, $df = 1$, $p < 0.001$) indicating more and faster gingival index improvement in test group (Group X) for both implant and non-implant sites. Test group (Group X) implants decreased in gingival index scores by 83% while implants in control group (Group A) decreased by 57%. The non-implant sites for control group (Group A) decreased by 23% and for test group (Group X) by 50%. The rate of change was faster for test group (Group X) implants than for control group (Group A) and faster than test group (Group X) non-implant sites. Test Treatment (rinse X) members' implants decrease in gingival index measured 26% versus 19% for those in control group (Group A).

[figure not shown]
Table 6 indicates a strong and statistically significant difference between implant and non-implant sites between and within groups – over time. Figure 9 illustrates the higher gingivitis index in test group (Group X) and greater and faster decrease of gingivitis in test group (Group X).

Table 6. Summary results of general linear model of gingival index measures.

Tests of Between-Subjects Effects

Gingivitis					
Source	Type III Sum of Squares	df	Mean Square	F	Sig.
Intercept	1207.001	1	1207.001	11073.258	0.000
implant	9.949	1	9.949	91.274	0.000
group	9.177	1	9.177	84.187	0.000
implant * group	8.613	1	8.613	79.021	0.000
Error	11.118	102	0.109		

Figure 9. Significant differential effects of mouthwashes on gingival index at implant sites. Both groups showed significant decreases in plaque, but the test group (Group X) reduced gingival index scores more and at a faster rate. Note the difference in gingival index scores at the beginning of the trial.

Implants and Plaque

Plaque scores (PS) for both implant and non-implant plaque scores were higher in the test group (Group X) (2.99 (0.071)) than in the control group (Group A) (2.35 (0.100)) at the first visit, $t = 5.45$, $df = 55$, $p < 0.001$. As with gingival index, PS decreased more for test group (Group X) patients (-0.799 (0.109)) than for control group (Group A) (-0.156 (0.064)) in both implant and non-implant sites, $t = 5.75$, $df = 55$, $p < 0.001$.

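### The implant-specific rinse benefit rests on time-averaged implant × group terms that match the baseline imbalance; on change it is not shown for MGI (p = 0.840, in a mislabelled Table 5) and not tested for plaque

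*Combined protocol and SAP*

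**What the plan says.** The section Global Probing Depths (GPD) sets the standard: an effective treatment shows itself in a treatment-by-time interaction.

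The site-level sections depart from it:

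- Differential Effects of Mouthwashes on Implants states that "implant sites improved at a faster rate under test rinse Treatment (rinse X) conditions for both gingivitis and plaque".
- Implants and Gingival Index gives F = 79.0, calls it a main effect, and reads it as "indicating more and faster gingival index improvement in test group (Group X) for both implant and non-implant sites". It adds that "Table 6 indicates a strong and statistically significant difference between implant and non-implant sites between and within groups", over time.
- The same section reports: "Test group (Group X) implants decreased in gingival index scores by 83% while implants in control group (Group A) decreased by 57" percent. Non-implant sites are given as 23% (control) and 50% (test). It then gives 26% versus 19% for the same two sets of implants.
- The caption of Table 7 takes the plaque implant × group term as the rinses acting differently by site.
- The table captioned "Table 5. Summary results of general linear model of probing depth measures for implant sites over time" is headed with GGI as its measure and contains the row "Time * implant * group 0.001 1 0.001 0.041 0.840". The text describing it lists a three-way interaction as notable and then says: "The three-way interaction is a false signal in that implant scores probe scores increased slightly in the test group (Group X").
- The Conclusions claim a benefit that favours implant sites over both placebo and non-implant sites, and say implants improved more and faster, with p < 0.001 for each.

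**The concern.** Whether the rinse helps implants more than teeth is a question about change. It needs the time × implant × group term. Table 6 and Table 7 are between-subjects tables: they average each patient's scores over visits and compare levels. A gap between arms that existed at Day 0 and persisted would make their implant × group rows significant with no treatment effect at all, and Table 1 shows just such a gap.

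The disease under study is peri-implant mucositis, so a benefit specific to implants is a headline conclusion. If the cited tests measure baseline imbalance, and the one test of the right kind is null and hidden under the wrong caption, that conclusion has no support in the report.

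**Working it through.** **Inputs.** Table 1 baseline means (27 control and 26 test patients); sums of squares (SS), F values and error terms from Tables 4 to 7; descriptive statistics from Table 3. There are 53 patients × 2 site types = 106 rows and 4 cells, hence error df 102. Let v = 2/27 + 2/26 = 0.151.

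**1. Reproduce the printed tests.** Table 6 implant × group: 8.613/(11.118/102) = 79.02. Table 7: 7.532/(49.62/102) = 15.48. Table 5: F(1,102) = 0.041 gives p = 0.840. All agree. F = 79.0 is therefore the interaction row of Table 6, not a main effect, and that table has no time row.

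**2. Number of visits averaged (T).** Tables 6 and 7 do not state it. The grand mean implied by the intercept is √(SS·v/16/T).

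| T | MGI | Plaque |
|---|---|---|
| 1 | 3.38 | 3.88 |
| 2 | 2.39 | 2.75 |
| 3 | 1.95 | 2.24 |

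The four-cell baseline means from Table 1 are 8.76/4 = 2.19 (MGI) and 10.92/4 = 2.73 (plaque). Scores fell, so an average over visits must lie below these. Only T = 3 does, and its plaque value is close to the three-visit average of 2.22 from Table 3.

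**3. Time-averaged contrast against baseline.** Size of the implant × group contrast = √(SS·v/3).

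- MGI: √(8.613 × 0.151/3) = 0.658. Baseline: (2.82 − 2.06) − (2.01 − 1.87) = +0.62.
- Plaque: √(7.532 × 0.151/3) = 0.616. Baseline: (2.84 − 2.77) − (2.99 − 2.32) = −0.60.

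From the Table 1 standard errors, ignoring pairing, the baseline contrasts have SE of about 0.08 and 0.18, so they lie about 7 and 3 SEs from zero. Carried unchanged through three visits they would give F of about 70 (3 × 0.62²/0.151/0.109) and 14.7 (3 × 0.60²/0.151/0.4865), against the printed 79.0 and 15.5.

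**4. Signs.** Table 4 pools MGI and plaque: its error SS, 60.738, equals 11.118 + 49.62. Its implant × group row (SS 0.018) gives the sum of the two contrasts, √(0.018 × 2 × 0.151/3) = 0.043. Its row "Implant * measure * group 16.127 1 16.127 54.166 0.000" gives their difference, √(16.127 × 2 × 0.151/3) = 1.274. The contrasts therefore have opposite signs; with Table 1 fixing MGI as positive, they are +0.658 and −0.616. The report reads both as favouring implants.

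**5. What Table 5 contains.** For the change from first to last visit, contrast (y3 − y1)/√2:

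- mean fall: √(15.113 × 2v)/4 = 0.534
- implant effect: √(1.507 × 2v)/2 = 0.337
- group effect: √(0.941 × 2v)/2 = 0.267
- three-way term, from F because the SS is rounded: √(0.041 × 2.737/102 × 2v) = 0.018 in size

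Table 3 gives a global fall of 0.49 for gingival index and 0.21 for probing depth, so 0.534 fits gingival index. Rebuilding the four cells:

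| Cell | Three-way negative | Three-way positive | Printed |
|---|---|---|---|
| Test implants | 0.831 | 0.841 | 83% |
| Control implants | 0.574 | 0.565 | 57% |
| Test teeth | 0.503 | 0.494 | 50% |
| Control teeth | 0.228 | 0.237 | 23% |

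The negative sign reproduces all four printed figures. They are falls in index points, not percentages. As shares of Table 1 baselines they are 0.83/2.82 = 29%, 0.57/2.06 = 28%, 0.50/2.01 = 25% and 0.23/1.87 = 12%.

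**6. Implant-specific effect on MGI.** The extra fall with the test rinse is 0.831 − 0.574 = 0.257 at implants and 0.503 − 0.228, about 0.276 unrounded, at teeth. The difference is −0.018, with SE √(2 × 0.0268 × 0.151) = 0.090 and 95% CI −0.018 ± 0.179, that is −0.20 to 0.16.

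**7. Pairing.** Error df 102 treats the implant and tooth averages of one patient as independent. The within-patient correlation r is not given. If the SE is multiplied by √(1 − r) on 51 df, the three-way p is 0.84, 0.82, 0.78 and 0.69 at r = 0, 0.25, 0.5 and 0.75. Time × group becomes 35.047/(1 + r): at r = 1, F is about 17.5 and p about 0.0001.

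**8. Plaque.** The slopes −0.151 and −0.463 compare arms at implants only. The statement that test-arm implants improved 57% more than teeth has no test and no control-arm counterpart. It would need a tooth slope of −0.463/1.57 = −0.295, whereas the test-arm global slope is −1.43/2 = −0.715. A mean over implants and teeth cannot lie outside both. The comparison is approximate, because the global analysis has 57 patients and the site analysis 53.

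**The case against.** The sentence quoted with F = 79.0 speaks of both site types, and the last claim about implants can be read as two pairwise statements: implants fell more than teeth, and more than control implants. Table 5 supports both for MGI change (time × implant F = 56.2, time × group F = 35.0). That is fair, and those statements can stay once tied to those terms. It does not rescue the claim of a benefit favouring implants or the Table 7 caption, which need the three-way term. The word softening the first conclusion does not extend to the later p < 0.001 sentence.

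The identity of Table 5 is inferred, GGI is the report's name for the global index, and figures are not visible in the text read here, so a probing-depth table might exist as an image. But the four-cell match and the size of the mean fall leave little doubt that the printed table is gingival index. The text also calls notable a term with p = 0.840 and describes a rise at test implants that the table does not contain.

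The percentages of baseline depend on Table 1, which has conflicts of its own (39 versus 42 test implants; 26 patients versus 18 + 9 + 2 = 29). The final figures should therefore come from the raw data.

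Finally, the between-arm MGI result on change is not baseline-adjusted; the only adjusted result is the global ANCOVA, p = 0.039. At implants the relative falls are nearly equal, 29% and 28%. That result should carry this qualification.

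**Conclusion.** The point holds. The significant terms cited for an implant-specific benefit have no time component and are about the size of differences present before treatment. On change, the benefit is not shown for MGI: difference −0.02 points, 95% CI about −0.20 to 0.16, p = 0.840. A modest effect is not excluded. For plaque no three-way test is reported, and the 57% figure fits poorly with the report's own global slope.

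This rests on three visits being averaged in Tables 6 and 7, which the intercepts support, and on Table 5 holding gingival index data, which its heading and rebuilt cells support. The null reading does not depend on how strongly site averages correlate within a patient, over an assumed range of 0 to 0.75. The global MGI treatment-by-time result is not affected. A main conclusion is wrong as written and must be corrected.

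**What to change.** 1. Stop citing Table 6 F = 79.0 and the Table 7 implant × group term as evidence of change.
2. Confirm Table 5 against the output and relabel it as MGI, correct the text that describes it, and supply the implant-site probing-depth model as a table.
3. Restate 83/57/50/23% as falls of 0.83/0.57/0.50/0.23 index points (29/28/25/12% of the Table 1 baselines), check them against raw data, and reconcile them with 26% and 19%.
4. Report time × group × implant for MGI and for plaque, with confidence intervals, from a model that accounts for implant and tooth averages coming from the same patient. Give a baseline-adjusted Day 90 analysis separately.
5. Reconcile the plaque figure of 57% with the global slopes, or remove it.
6. Withdraw the implant-favouring conclusion as a rinse effect: state not shown for MGI and not tested for plaque, unless the new models show otherwise. Statements that MGI fell more in the test arm, and more at implants than at teeth in both arms, may stay if tied to Table 5's time × group and time × implant terms and qualified for baseline imbalance.

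The cost is two site-level models re-run on existing data, one table added, and captions, percentages and one conclusion corrected. The sponsor loses the implant-specific claim unless the models support it, and keeps the between-arm MGI result.

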Samples for microbiome analysis were collected at baseline (Visit 1), Day 14 (Visit 2), and Day 90 (Visit 4). Before collecting samples, each patient was asked to rinse with plain water prior and rest for 5 minutes. Sample collection was performed by gently wiping the buccal and tongue mucosa separately 10 times with three different cotton swabs. Samples were allowed to air dry at room temperature and individually placed in labeled containers with the patient's unique sequential subject identification number and day of collection. These samples were stored in a secure location at -20°C until utilized for microbiome analyses.

[4] Study Design Table

Protocol Study Design and Schedule of Assessments

Evaluation	Screening (0-2wks to Baseline)	Baseline (Visit 1) Day 0	Visit 2 Day 14 (± 3 d)	Visit 3 Day 45 (± 7 d)	Visit 4 Day 90 (± 7 d)
Informed Consent	x				
Inclusion / Exclusion	x	x			
Demographics	x				
Pregnancy Test		x			x
Medical History / Update	x	x	x		x
Medications / Update	x	x	x		x
Periodontal History	x		x		x
Oral Examination	x	x	x		x
Collect Specimen w Swab		x	x		x
Modified Gingival Index / MGI		x	x		x
Bleeding On Probing / BOP	x				x
Probing depth	x	x			x
Turesky modification Plaque Index		x	x		x
Scaling	x				
Eligibility	x				
X-rays		x			x
Enrollment / Randomization		x			
Dispense oral hygiene kit / Diary		x			
Schedule next appt	x	x	x		
Collect residual oral hygiene kit with Diary and distribute oral hygiene kit with Diary for next phase			x	x	
Collect residual oral hygiene kit / Diary					x

[5] Protocol Synopsis

1. Study Title: The Efficacy and Safety of stabilized chlorine dioxide mouth rinse in Therapy of Peri-implant mucositis
2. Study Design: Single Center, randomized, double blind masking, parallel, two-arm clinical study.
3. Objective: The purpose of this study was to analyze efficacy of stabilized chlorine dioxide as a chemical adjuvant for treatment of peri-implant mucositis in a non-surgical treatment protocol with a 3-month follow-up.
4. Study Treatments: 1) Stabilized chlorine dioxide (associated with periodontal basic therapy); and 2) control (placebo associated with periodontal basic therapy).
5. Number of Patients: A total of 54 patients in one clinical site at Stony Brook were randomized, 27 patients received 1) Stabilized chlorine dioxide (associated with periodontal basic therapy); and 27 patients received 2) control (placebo associated with periodontal basic therapy).

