- a) Gingival inflammation (MGI)

Secondary analyses were the comparison of data with respect to product effectiveness:

- a) Reduction in bleeding on probing (BOP) and Turesky modification of the Quigley-Hein Plaque Index (PI) grading on all natural teeth in the dentition

The primary statistical analytic framework was the repeated measures analysis of variance on three primary outcomes: probing depth, gingival index, and plaque. The primary hypothesis tested was the treatment by time interaction, i.e., did one treatment work better during the observations of these three outcomes? In other words, not just the total change, but also the rate of that change might differ between treatments. The proposed analysis was based on data that were generally normally distributed and similarly. If not, data transformations or link functions were used.

Outcomes

Raw data were collected from examinations of each tooth with regard to probing depth, gingival index, and plaque. Data were collected over three time periods, recorded into patient files, and transferred to Excel Workbooks, with one Workbook per patient. Each Workbook contained three tabs, one for each visit.

The raw data were combined as two levels of indexes for the three measures. The first outcome was a global score index of probing depth, gingival index, and plaque measurement. The global index was derived from individual tooth scores for each measure divided by the number of teeth measured. The second index derived from the same raw data described the three measures in terms of average scores for implant and non-implant teeth.

For the second analysis, implanted tooth data were separated from normal teeth data within each patient. Implant scores for each patient were averaged for probing depth, gingival index, and plaque scores. If a patient had one implant, each score was identical to the single measurement. With more than one implant, a single implant score for each patient was derived from averaging each of the three measures over the three observation periods. Likewise for each patient, the non-implanted teeth measures were averaged for each of the three times of assessment.

Individual patient data of the averages of the implant and non-implant teeth were calculated for each time period and transferred to a master data sheet.

Data Management and Statistical Analysis

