The patients' data on the three measures were recorded within the Excel Workbooks under three tabs representing the first, second, and third clinical observation periods. So each tab recorded three measures. The first and last tabs recorded probing depth, gingival index, and plaque. The second visit included only gingival index and plaque. Each patient had an individual Excel Workbook. Data were sorted into analysis format through two Excel macros that created a single master data for global scores and a single one for implant and non-implant scores. Data files were saved in comma separated value (csv) format in both wide and long formats for R and SPSS data management, inspection, cleaning, and analyses.

Since many individual variable distributions varied substantially from normal, a gamma log-link function was applied to reduce bias in most statistical tests.

Label Key and Lot #s for Peri-Implant Mucositis Study with Stony Brook University

Rowpar Pharmaceuticals, Inc., released the test material label codes after completion of the clinical study and statistical analysis of the data. The products were labelled as follows:

Study Number: SBU-RPR-Peri-Implant Mucositis-2018

Oral Rinse A: ClōSYS Placebo Oral Rinse, Lot #: 2-80516

Oral Rinse X: ClōSYS® Ultra Sensitive (Unflavored) Oral Rinse, Lot #: 8122A 14-80430

Results

Patients

Fifty-two percent (29/56) of patients in both groups had only one implant. Patients in the control group (Group A) had a total of 47 implants: 11 patients had just one implant, 13 had 2, 2 had 3, and 1 had 4 implants. In the test group (Group X), there were 42 total implants in 26 patients: 18 had 1 implant, 9 had 2, and 2 had 3 implants (see Figure 1). Table 1 gives average values (and standard error of the mean) of Gingivitis Index, Plaque score, and Probing depth at baseline.

Figure 1. Bar chart of numbers of implants per person in control group (Group A) and test group (Group X).

[figure not shown]

Table 1. Patient dental measures at baseline.

		n of patients	n of implants	Modified Gingivitis Index (MGI) (sem)	Plaque score (PS) (sem)	Probing Depth mean (sem)
Control Group (Group A)	implants	27	47	2.06 (0.048)	2.77 (0.115)	3.40 (0.109)

	non-implanted teeth			1.87 (0.039)	2.32 (0.101)	2.72 (0.099)
Test Group (Group X)	implants	26	39	2.82 (0.049)	2.84 (0.057)	2.447 (0.080)
	non-implanted teeth			2.01 (0.028)	2.99 (0.078)	2.65 (0.079)

Global Score Analyses

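### The 83%, 57%, 50% and 23% gingival-index decreases appear to be MGI points printed as percentages, and they contradict the 26% and 19% given in the same paragraph

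*Combined protocol and SAP*

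**What the plan says.** Section 11 (Statistical Evaluation) lists one measure under the primary objective: "Gingival inflammation (MGI"). The Results subsection on implants and gingival index then reports, in one paragraph:

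- Implants: test "implants decreased in gingival index scores by 83% while implants in control group (Group A) decreased by 57" per cent.
- Teeth: "The non-implant sites for control group (Group A) decreased by 23% and for test group (Group X) by 50" per cent.
- Implants again, three sentences after the first pair: "implants decrease in gingival index measured 26% versus 19% for those in control group (Group A").

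The same paragraph cites F = 79.0 as a main effect showing more and faster improvement. Table 1 gives baseline MGI of 2.82 (test implants), 2.06 (control implants), 2.01 (test teeth) and 1.87 (control teeth). The global gingival index subsection gives whole-mouth reductions of 27.3% (test) and 20.4% (control). The Conclusions say the test rinse seemed to favour implant sites over both placebo and non-implant sites.

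**The concern.** Two different pairs of percentages are given for the same quantity, and the larger pair is also hard to square with the whole-mouth figures. If test implants fell by 83% and test teeth by 50%, a test whole-mouth fall would lie between 50% and 83%, not at 27.3%. If control implants fell by 57% and teeth by 23%, the control whole-mouth fall would lie between 23% and 57%, not at 20.4%.

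Implants are the diseased sites. A reader who takes 83% against 57% at face value sees near-resolution of inflammation under the test rinse and a gap of 26 percentage points between the arms. A unit error would make both the size of the fall and that gap wrong on the primary outcome.

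**Working it through.** **Inputs.** Baselines are from Table 1. Sums of squares (SS) are from Tables 5 and 6. Patients: 26 test and 27 control (Table 1), each with an implant score and a tooth score. That gives 2 × 53 = 106 scores in four cells, and 106 − 4 = 102, the error df printed in both tables. Sum of 1/n over the cells = 2/26 + 2/27 = 0.1510.

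**What Table 5 holds.** Its title says probing depth, but its measure label is GGI. The accompanying text calls a three-way interaction notable and says probing depth did not change. The table shows a three-way term with p = 0.840 and a Time term with F = 563.159. It fits gingival index, not the text around it.

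**Step 1: test the two readings against Table 5.** With a normalised linear contrast over three visits, L = (last − first)/√2, each term has SS = (signed sum of the four cell falls)² / (2 × 0.1510).

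- Points reading: signed sums are 2.13 (all four falls), 0.67 (implants − teeth), 0.53 (test − control) and −0.01 (three-way).
- Percentage reading: falls are 0.83 × 2.82 = 2.341, 0.57 × 2.06 = 1.174, 0.50 × 2.01 = 1.005 and 0.23 × 1.87 = 0.430.

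| Term | Table 5 | Points | Range from rounding of points | Percent of baseline |
|---|---|---|---|---|
| Time | 15.113 | 15.02 | 14.74–15.31 | 81.1 |
| Time × implant | 1.507 | 1.49 | 1.40–1.58 | 14.3 |
| Time × group | 0.941 | 0.93 | 0.86–1.00 | 10.0 |
| Three-way | 0.001 | 0.0003 | 0–0.003 | 1.16 |

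The points reading matches all four terms and the percentage reading none. Percent of final value (30.7 / 3.4 / 2.4 / 0.15) and log change (44.4 / 5.7 / 4.0 / 0.28) also fail.

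**Step 2: back-solve.** The contrasts √(2 × SS × 0.1510) are 2.136, 0.675, 0.533 and 0.017. With a negative three-way term, the falls are 0.832 (test implants), 0.574 (control implants), 0.503 (test teeth) and 0.228 (control teeth), which round to the printed digits. With a positive term they are 0.840, 0.565, 0.494 and 0.237. An SS does not carry its sign, so this step shows agreement to within 0.01 point and no more.

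**Step 3: separate check from Table 6.** The signed sums of visit-averaged cell means are √(SS × 0.1510/3): 7.794 (intercept), 0.708 (implant), 0.680 (group) and 0.658 (implant × group). Test-implant mean = (7.794 + 0.708 + 0.680 + 0.658)/4 = 2.46. The other cells are 1.79 (control implants), 1.78 (test teeth) and 1.77 (control teeth). Under a linear decline:

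| Cell | Table 6 implies | Points | Percentages |
|---|---|---|---|
| Test implants | 2.46 | 2.41 | 1.65 |
| Control implants | 1.79 | 1.78 | 1.47 |
| Test teeth | 1.78 | 1.76 | 1.51 |
| Control teeth | 1.77 | 1.76 | 1.65 |

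For test implants the linear assumption is not needed. An 83% fall ends at 2.82 × 0.17 = 0.48. A three-visit mean of 2.46 would then need a Day 14 value of 3 × 2.46 − 2.82 − 0.48 = 4.08, far above baseline. A fall of 0.83 points needs 3 × 2.46 − 2.82 − 1.99 = 2.57, between baseline and final.

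**Step 4: implied percentages (points / Table 1 baseline).**

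- Test implants: 0.83/2.82 = 29.4%. Printed 83%, ratio 2.8.
- Control implants: 0.57/2.06 = 27.7%. Printed 57%, ratio 2.1.
- Test teeth: 0.50/2.01 = 24.9%. Printed 50%, ratio 2.0.
- Control teeth: 0.23/1.87 = 12.3%. Printed 23%, ratio 1.9.

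The gap between arms at implants is 29.4 − 27.7 = about 1.8 percentage points, against 83 − 57 = 26 printed. In points it is 0.83 − 0.57 = 0.26. Implied Day 90 implant scores are 2.82 − 0.83 = 1.99 (test) and 2.06 − 0.57 = 1.49 (control).

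**Step 5: the second printed pair.** 26% and 19% need falls of 0.26 × 2.82 = 0.73 and 0.19 × 2.06 = 0.39 points. With 0.50 and 0.23 at teeth, these give SS of 11.39 / 0.52 / 1.24 / 0.017, which do not fit Table 5.

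**The case against.** The fair case on the other side has five parts.

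- **The percentages in Step 4 are reconstructions.** They assume a linear contrast in a table that names no contrast type and carries the wrong title. They also do not reconcile with the whole-mouth section. With 20 natural teeth (the entry minimum) and 47/27 = 1.74 implants per control patient, the control whole-mouth fall would be (1.74 × 0.57 + 20 × 0.23)/(1.74 × 2.06 + 20 × 1.87) = 13.6%, against 20.4% printed. The global analysis uses 57 patients with minimum scores of 0 at later visits, while Table 5 implies 53. This stands: the reconstructed figures are not the correct ones, only those that Tables 1 and 5 imply.
- **A treatment difference survives.** The Time × group term in Table 5 (F = 35.047) and the 0.26-point difference do not depend on the percentages. This stands. A reader might infer that there is no effect at implants; the documents do not support that. Near-equality holds on the percentage scale only, which divides by unequal baselines.
- **The Conclusions cite no percentage.** Their general claim of advantage covers plaque and gingival index overall and rests on p-values, ANCOVA for plaque, difference scores and slopes. A reader might infer that this claim falls with the percentages. It does not; the implant statement is a separate sentence.
- **The implant comparison is the document's second analysis.** The global MGI result is untouched by this error. This also stands.
- **The baseline imbalance is disclosed** in the note to Figure 9 and in the Conclusions. True, but that does not correct the units.

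None of this explains how 83% and 26% can both be the fall at test implants.

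**Conclusion.** The figures are wrong as written. Two incompatible pairs of implant decreases stand in one paragraph, and the larger set is best explained as MGI points printed as percentages. This rests on Table 5 being a linear contrast of gingival index in 26 and 27 patients, and it is supported separately by Table 6.

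On the Table 1 baselines the overstatement is about 2.8-fold for test implants and about twofold for the other three cells. A reader might infer a uniform threefold inflation. That holds only against the 26% and 19% pair (83/26 = 3.2, 57/19 = 3.0), and that pair is not validated either. Neither it nor the reconstructed set can be taken as correct without the raw data.

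For gingival index, an extra benefit at implants is not supported. The "Time * implant * group" term in Table 5 has p = 0.840, and the difference in fall is about the same at implants (0.26) and teeth (0.50 − 0.23 = 0.27). The F = 79.0 cited for faster improvement is the implant × group term of Table 6 (79.021), which tests levels averaged over visits, not change. This finding does not extend to plaque.

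**What to change.** 1. Report the four changes in MGI points in place of 83%, 57%, 50% and 23%.
2. Recompute one set of percentages from the raw data, stating the baselines and the patients included, and reconcile it with the whole-mouth 27.3% and 20.4%.
3. Delete 26% and 19%, or explain how they were derived.
4. Relabel Table 5 as gingival index and supply the probing-depth table that its text describes. Describe F = 79.0 as the implant × group term on visit-averaged levels.
5. Revise the statement in the Conclusions of a particular benefit at implant sites, so that for gingival index it matches the corrected figures and the non-significant three-way term.

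As an addition rather than a correction, a baseline-adjusted Day 90 implant MGI difference with a 95% CI can be computed from existing data. It would be useful because the reported ANCOVA for this outcome covers only the whole-mouth index.

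The cost is re-tabulation of data already held. The stated effect at implants becomes less favourable.
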